10.2 Recording of Adverse Events

All AEs occurring during the treatment period starting after the first vaccination at Visit 1 until termination of Visit 5 (day 56) observed by the investigator or reported by the subject (verbally or in the subject diary), will be recorded, whether or not related to the study treatment.

AEs will be requested at each visit during the treatment period up to Visit 5 (day 56) and additionally solicited by a subject's diary for 7 days after each vaccination. (see section 11.7)

The subjects will be asked generally (e.g. "How are you?") as well as specifically (e.g. "Have you experienced any problems since the last visit?").

The investigator must record all adverse events in the eCRF. One single adverse event page must be used per adverse event, from start to resolution, stating the following information: AE description, date of onset and end date, severity, relatedness, seriousness and action taken. Please consider definitions of section 10.1. Follow-up information should be provided as necessary.

If possible, the investigator should record the diagnosis. If a diagnosis is not available, the investigator should record each sign and symptom as individual adverse events. However, as soon as a diagnosis becomes available, all signs and symptoms should be summarised and replaced by the underlying adverse event term (e.g. common cold instead of separate AEs for headache, rhinorrhoea, arthralgia, fever etc.)

The AE should be documented stating the highest severity (i.e. if an AE goes from mild severity to moderate severity or vice versa, the whole episode of the AE should be reported with the moderate severity). Please consider Table 5 and 6 for grading local injection site reactions and systemic reactions.

For causality reporting purposes, the categories "definitely", "probably" and "possibly" qualify an event as "suspected" adverse reaction. AEs with missing causality assessment will be regarded as possibly related unless further specified.

Any medical condition that is present at screening will be considered as medical history and not reported as an AE. However, if the subject's condition deteriorates at any time during the study, it will be recorded as an AE.

It will be left to the investigator's clinical judgment to decide whether an AE requires the subject's removal from the study. In case of discontinuation, the subject will undergo an early termination visit.

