Furthermore, participants were requested to keep a study diary in order to record all local and systemic symptoms and any adverse event occurring during the first two weeks after vaccination starting with the first entry 6 hours (± 1) after vaccination. The subjects themselves recorded the assessments once daily at the same time each day. Completeness and accuracy of self-reported symptoms and side effects were verified at each visit by a study-related physician. Diaries were reviewed together with the particular participant at each visit and participants were interviewed for any adverse events. Diaries had to be signed by both the particular participant and the reviewing physician at the end of each vaccination period to confirm and ensure completeness and reliability of self-reporting. The investigator collected the diaries at each visit and new ones were dispensed after vaccination.

Solicited and non-solicited adverse events (AEs) were reported separately. Solicited AEs included pyrexia, flu like illness, headache and injection-site- related side effects (erythema, swelling, induration and pain).

In general, MV-CHIK vaccine had an acceptable tolerability profile. All adverse events observed were treatment emergent AEs and were recovered without any sequelae before or at study end.

The most frequently solicited AEs were headache (57.1%), injection site pain (50.0%), influenza like illness (45.2%), vaccination site pain (40.5%), fatigue (38.1%), nausea (31.0%), myalgia (26.2%) and arthralgia (23.8%). The most frequently related solicited AEs were injection site pain (50.0%), vaccination site pain (40.5%), headache (28.6%) and fatigue (23.8%).

Unsolicited AEs were AEs with none of the preferred terms of solicited AEs. 28 subjects (66.7%) had a total of 73 unsolicited AEs. Two subjects (4.8%) had two severe unsolicited AEs, five subjects (11.9%) had seven related unsolicited AEs and 19 subjects (45.2%) reported 33 unsolicited AEs where an action was taken. Two subjects (4.8%) reported two serious unsolicited AEs. The most frequently unsolicited AEs were nasopharyngitis (26.2%) and oropharyngeal pain (11.9%).

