11.7 Subject Diary

The subjects will be instructed to complete a diary for 7 days after each vaccination to document local and systemic tolerability as well as body temperature.

Solicited local and solicited systemic AEs will be assessed by the subjects themselves by checking for presence of the listed symptoms and measuring the size of the affected area where appropriate (a template will be provided for local reaction grading, as shown in Appendix 1). The diary will also provide space for recording unsolicited AEs and concomitant medication.

Recording should be done approximately at the same time each day, starting on the day of vaccination. The first entry should be made 6 hours ± 1 h after vaccination at Visit 1 and Visit 3.

The subjects' diaries will be collected and verified for completeness by the investigator at Visit 2 and Visit 4. Any AE recorded in the subject diaries will be entered in the eCRF by the investigator or authorised delegates. The investigator will re-evaluate the severity of the reported local and systemic AEs according to the below Tables 5 and 6.

Diary solicited systemic AEs include: nausea, vomiting, headache and fatigue, also to be documented in the eCRF.

In addition, body temperature will be recorded daily for 7 days and fever will be graded by the investigator according to the FDA Guidance for Industry. For details see below Table 6.

Table 5: Grading of Local Reactions

Local reaction to injectable product	Mild (grade 1)	Moderate (grade 2)	Severe (grade 3)	Potentially life threatening (grade 4)
Pain	Does not interfere with activity	Interfere with activity or repeated use of non-narcotic pain reliever	Prevents daily activity or repeated use of non-narcotic pain reliever	Emergency room (ER) visit or hospitalisation
Tenderness	Mild pain to touch	Pain with movement	Significant pain at rest	ER visit or hospitalisation
Erythema/ Redness¹	≤ 5 cm	5.1–10 cm	> 10 cm	Necrosis or exfoliate dermatitis
Swelling²	≤ 5 cm and does not interfere with activity	5.1–10 cm or interfere with activity	> 10 cm or prevents daily activity	Necrosis
Itching	Does not interfere with activity	Interferes with activity or repeated use of non-narcotic pain reliever	Prevents daily activity or repeated use of anti-inflammation and pain-relieving ointment	Emergency room (ER) visit or hospitalisation

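### The diagnosis rule in protocol 10.2 has no exemption for diary-solicited reactions and conflicts with 11.7 and 12.3, so a replaced symptom may drop out of the by-symptom solicited tables

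*Combined protocol and SAP*

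**What the plan says.** Protocol 10.2 (Recording of Adverse Events) prefers a diagnosis to its symptoms. Without one, symptoms stay separate: "If a diagnosis is not available, the investigator should record each sign and symptom as individual adverse events". Once one is available, the instruction changes: "all signs and symptoms should be summarised and replaced by the underlying adverse event term". The example is "common cold instead of separate AEs for headache, rhinorrhoea, arthralgia, fever etc". The same section names the subject diary as a source of adverse events, but it does not set diary-solicited symptoms apart.

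Protocol 11.7 (Subject Diary) points the other way for diary data: "Any AE recorded in the subject diaries will be entered in the eCRF by the investigator or authorised delegates". It then names terms: "Diary solicited systemic AEs include: nausea, vomiting, headache and fatigue, also to be documented in the eCRF". On fever it says that "body temperature will be recorded daily for 7 days and fever will be graded by the investigator".

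Protocol 12.3 describes the solicited summary as covering the local and systemic events collected in the diaries over 7 days, by grade and treatment group.

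SAP 6.2.1 plans solicited tables by symptom, and by symptom and severity. SAP 6.2.2 takes the adverse event endpoints from the adverse event records in the database and uses the treatment group total as the denominator.

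**The concern.** The rate of solicited adverse events is a named secondary endpoint (protocol 6.2.2, SAP 1.3.2) and is the trial's reactogenicity result for five small groups. If site staff apply 10.2 to a diary symptom, headache becomes part of a diagnosis and is no longer a headache record. If they apply 11.7, it stays. Both follow the protocol, yet they give different by-symptom tables. The tables would not show which rule was used.

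**Working it through.** **1. The recording rules side by side**

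| Place | Diary headache, no diagnosis | Diary headache, diagnosis made |
|---|---|---|
| Protocol 10.2 | Own record | Replaced by the diagnosis |
| Protocol 11.7 | Entered in the eCRF | Entered in the eCRF; replacement not mentioned |
| Protocol 12.3 | In the 7-day diary summary | In the 7-day diary summary |

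The rules agree in the first column and conflict in the second. Of the terms in the 10.2 example, headache is a named solicited term in 11.7, and fever comes from the daily diary temperature. Rhinorrhoea and arthralgia are not named in 11.7. Nothing in either document ranks the sections.

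**2. Can a replaced symptom return to the tables through the SAP?**

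- Tables 1.4.8, 1.4.9, 1.4.11 and 1.4.12 (SAP 7.1) count subjects with solicited events by symptom.
- The solicited listings from 1.4.19 onward (SAP 7.2) carry adverse event record fields such as record ID, term and causality. No diary listing is planned.
- The temperature table (1.4.41) is by visit, and SAP 6.4 limits vital signs to screening, Visit 3 and Visit 5. It does not show diary temperature.
- The nearest handling rule (SAP 2.8) covers a missing solicited/unsolicited assignment, not a diagnosis that replaced a solicited symptom.

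So no route back is planned.

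**3. Direction**

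The denominator is the fixed group total. Removing a symptom record can lower the count of subjects with that symptom or leave it unchanged. It cannot raise it.

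**4. Size (illustration only)**

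The documents state no expected rate for this trial and no share of symptoms replaced, so there is no planned figure to reproduce. Two headache rates from protocol 4.4 serve as a low and a high case:

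- MV-CHIK-101: 57.1% (24/42).
- MV-CHIK-202: 42 subjects, 19.7%. The 17 control subjects are 34.0%, so there are 17/0.34 = 50 controls. Then 263 − 50 = 213 and 42/213 = 19.7%.

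Let *p* be the true rate and *f* the assumed share of subjects with headache whose headache is replaced. The tabulated rate is *p* × (1 − *f*).

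| Assumed *f* | *p* = 19.7% reads | *p* = 57.1% reads |
|---|---|---|
| 0 | 19.7% | 57.1% |
| 5% | 18.7% | 54.3% |
| 10% | 17.7% | 51.4% |
| 50% | 9.9% | 28.6% |

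For a group of 12, the chance of losing at least one headache subject is 1 − (1 − *pf*)^12. At *f* = 10% this is 1 − (1 − 0.0197)^12 = 21% in the low case and 1 − (1 − 0.0571)^12 = 51% in the high case. One subject is 1/12 = 8.3 percentage points.

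**The case against.** The strongest reply is that 11.7 and 12.3 are the specific rules for diary data and 10.2 is the general one, so the specific rules should prevail. The rule in 10.2 also acts only when a diagnosis is made, and its one example is an intercurrent illness, not a vaccine reaction. An undiagnosed headache after vaccination is untouched. Completed diaries are kept as source records (protocol 15.1), so the information is not destroyed. All of this stands, and it makes the loss a risk and not a certainty. It does not remove the conflict: the precedence is a reasonable guess that no text confirms, and no planned table or listing uses the diaries directly.

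The effect on overall counts is also limited. The replacing diagnosis still counts in the combined summary (SAP Table 1.4.2). A subject leaves the count of those with any solicited event only if no other solicited event remains, and local reactions are common (injection site pain 50.0% in MV-CHIK-101). SAP 6.2.1 places the between-group test in the overview table, so the tests are less exposed than the by-symptom rates.

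Two stronger inferences are tempting and are not supported:

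- *Replacement shrinks the dose difference.* Protocol 4.4.1 says that overall, related and local events rose with dose. It does not say so of multi-symptom systemic reactions, and nothing shows that replacement would fall more on the high-dose groups.
- *A flu-like diagnosis moves a solicited reaction into the unsolicited tables.* Flu-like illness was solicited in MV-CHIK-101 ("influenza like illness (45.2"%), but it was reported there alongside headache and fatigue, not in their place. The list in 11.7 is worded as open, and the diary form is not among the documents. How such a term would be classified is not established.

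**Conclusion.** The conflict between 10.2 and 11.7/12.3 is real and unresolved. Where a diagnosis replaces a diary-solicited symptom, that symptom may drop out of the by-symptom solicited tables, and those rates can then only be too low.

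The size is unknown because the documents give no value for the replaced share. The 10% case is an assumption. The base rates are not forecasts either: MV-CHIK-101 had three injections, a two-week diary and control subjects among its 42, against two injections and a 7-day diary here. A reader might go further and multiply the phase I flu-like illness rate into the headache or fatigue rate to obtain a large loss. That needs an overlap and a replacement frequency that the documents do not report.

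This is a cheap improvement to a secondary endpoint. It is not a demonstrated bias, and it does not touch the primary immunogenicity comparison.

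**What to change.** Add to protocol 10.2:

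> *This rule does not apply to solicited local and systemic symptoms or temperature recorded in the 7-day diary. Each is kept in the eCRF as an individual solicited adverse event with its own grade and dates, even if a diagnosis is also recorded.*

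Add to SAP 6.2.2 that the solicited tables count these records whether or not a diagnosis was added.

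The cost is one sentence in each document and a line of eCRF guidance. No visit, sample or treatment changes. The downside is that one episode may appear in both the solicited and the unsolicited tables, which a footnote can explain.

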10.3 Reporting of Serious Adverse Events

The investigator should report all SAEs occurring during the treatment period (whether or not related to the IMP) within 24 hours of the site study team becoming aware of the event, to the Assign Safety Desk by completing an SAE Report Form.

The completed SAE Report Form should be submitted to the Assign Safety Desk either by fax or as pdf per e-mail:

Fax: PPD [REDACTED]

Email: PPD [REDACTED]

For urgent questions, please call the 24-hours Safety Hotline: PPD [REDACTED]

Under certain circumstances, the first notification can be done by phone, nevertheless, a written Serious Adverse Event Report Form should be submitted for confirmation to Assign Safety Desk.

After the initial SAE report the investigator will follow up proactively each subject and provide further information like copies of hospital case reports, laboratory reports or autopsy reports, to the Assign Safety Desk within 24 h after receipt.

Assign Safety Desk will assess initial and follow-up SAE reports from the site for expectedness, which will be determined based on the most recent edition of the Investigator's Brochure.

Reports of suspected unexpected serious adverse reactions (SUSARs) will be reported in an expedited manner to the regulatory authorities as required per local regulations within the required time frame.

The original copy of the SAE Report Form and the fax confirmation sheet must be kept with the documentation at the study site. Each SAE has also to be documented in the eCRF as a serious adverse event in the corresponding AE section.

10.4 Follow-up of Adverse Events

During and following a subject's participation in a clinical trial, the investigator will ensure that adequate medical care is provided to the subject for any adverse events, including clinically significant laboratory values related to the trial.

All non-serious and serious adverse events will be followed until the subject has recovered, stabilised, recovered with sequelae or died until end of the study.

Follow-up information about a previously reported SAE must also be reported within 24 hours of the investigator receiving it. The initial SAE report form should be used, stating that this is a follow-up report to the previously reported SAE and giving the number and date of the follow-up report. The information provided should describe whether the event has resolved or continues, if and how it was treated, and whether the subject continued or discontinued study participation, if not already stated in the initial report.

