Acute disease is most often characterised by the acute onset of high fever ($>102^{\circ}\text{F}/39^{\circ}\text{C}$). The fever typically lasts from several days up to 2 weeks. Other signs and symptoms may include headache, diffuse back pain, myalgias, nausea, vomiting, polyarthritides, rash, and conjunctivitis. After the onset of fever, the majority of infected persons develop severe, often debilitating polyarthralgia. Joint symptoms are usually symmetric and occur most commonly in wrists, elbows, fingers, knees, and ankles but also more proximal joints. The lower extremity arthralgias can be severely disabling resulting in a slow, broad based, halting gait that can persist for months. The patients may suffer from severe pain, tenderness, swelling and stiffness and they cannot perform normal tasks or go to work. Acute symptoms of chikungunya fever typically resolve within 7 to 10 days. Following the acute phase, a number of patients continue to experience prolonged symptoms, lasting several weeks to months, including fatigue, incapacitating joint pain, and tenosynovitis or oedematous polyarthritides. Chronic

disease is defined by symptoms that persist for more than 3 months [CDC/PAHO Chikungunya virus, 2011].

The frequency of persons reporting persistent symptoms varies substantially by study and the time that had elapsed between symptom onset and follow-up. Studies from South Africa note that 12%–18% of patients will have persistent symptoms at 18 months and up to 2 to 3 years later. More recent studies in India revealed that the proportion of patients with persistent symptoms at 9-12 months was 22% and additional 22% reported symptoms for more than one year (Paul BJ, 2011).

Data from La Réunion have found that as many as 60% of patients complained of persistent symptoms 36 months after disease onset. In almost one half of these patients the joint pain had negative impact on their everyday life and on their ability to work (Schilte C, 2013).

During 2005-2006 several European countries reported imported cases from travellers returning from the Indian Ocean region including France (808 imported cases). A detailed follow up of 47 patients that returned to Marseilles. 38 patients remained symptomatic after the tenth day with severe joint pain and tenosynovitis with a dramatically limited ability to ambulate and carry out activities in daily life (Simon F, 2007).

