4.6 Benefit/Risk Assessment

General

Potential risks that are frequently associated with vaccination are the occurrence of local reactions such as oedema, induration and erythema, transient local pain or tenderness at the injection site as well as mild to moderate headache, myalgia, flu-like symptoms or fatigue. Vaccines have been known to induce allergic and anaphylactic reactions apart from reactions at the vaccination site and systemic flu-like reactions. Additionally, needle picks for blood sampling may cause discomforts and local reactions.

MV-CHIK Related

As described above, adverse events (AEs) previously reported with MV-CHIK include injection site pain, headache, fatigue, and joint pain or arthralgia. Refer to the current version of the Investigators' Brochure for more detail.

Potential for Severe Adverse Reaction

In the past, a live virus vaccine against Chikungunya virus, which was based on an attenuated Chikungunya-strain was associated with mild, transient arthralgia in immunised individuals. The MV-CHIK vaccine is based on live measles virus and contains no live Chikungunya virus. Therefore, induction of chikungunya-like symptoms is not expected. However, the subjects will be monitored for occurrence of arthralgia, an adverse event of special interest (AESI).

Potential Benefit

If the clinical development of MV-CHIK is successful, the potential benefit of MV-CHIK vaccination would be life-long protection against Chikungunya infection helping people, who are at risk of acquiring a possibly life-threatening infection with CHIKV.

A boost in measles immunity may be an additional benefit.

Conclusion

The benefit risk ratio is considered favourable.

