6.4 Study Flowchart

6.5 Study Procedures

Table 2: Study Procedures

Visit	Screening	Treatment Period					Follow up Period		ET
		V1	V2	V3	V4	V5	V6	V7	
Study Day	-28 to -1	0	14 ±1	28 ±5	42 ±5	56 ±5	182 ±14	365 ±14	(7)
Informed Consent	X								
Inclusion/Exclusion Criteria	X	X							
Medical History	X	X							
Vaccination History	X								
Vital Signs (1)	X	X		X			X		X
Physical Examination (2)	X	X		X			X		X
Adverse Events (3)		X	X	X	X	X			X
Concomitant Medication (4)	X	X	X	X	X	X			X
Clinical Laboratory (5)	X			X			X		X
Pregnancy Test	X	X		X			X		X
Study Treatment (8)		X		X					
Dispense subject diary		X		X					
Collect subject diary			X		X				X
Local Tolerability (6)		X	X	X	X	X			X
Immunogenicity (PRNT ₅₀)		X		X		X	X	X	X
T-cell Immunity		X	X	X	X	X			X
CHIKV-antibodies (ELISA)		X		X		X	X	X	X
Measles-antibodies (ELISA)		X		X		X			X
Serum collection for passive transfer		X		X		X		X	X

(1) Assessment of vital signs will include systolic and diastolic blood pressure, pulse rate and body temperature

(2) A full physical examination will be performed at screening and a system based physical examination will be done at Visit 1, 3 and 5, if necessary according to findings in a symptom-directed physical examination

(3) Conditions/symptoms noted prior to first IMP administration will be reported as medical history and not as AEs, At Visit 6 and 7 AEs will not be recorded as subjects are allowed to participate in other clinical studies during the follow-up period.

(4) Medications administered within 30 days prior to screening until end of treatment period will be documented as concomitant medication.

(5) Clinical Laboratory parameters include:

- Virology: HB s-Ag, anti-HB c-Ab, anti-HC-Ab, HIV-Ab (only once at screening)
- Haematology: haemoglobin, haematocrit, erythrocyte count, differential and total white blood count, platelets
- Chemistry: creatinine, potassium, sodium, calcium, AST, ALT, alkaline phosphatase, bilirubin
- Coagulation parameter: prothrombin time (PT), activated partial thromboplastin time (aPTT), fibrinogen
- Urinalysis: pH-value, glucose, protein, bilirubin, urobilinogen, blood, leucocytes esterase, nitrite, ketone and specific gravity. In case of abnormal findings, a microscopy will be done for confirmation.

Please refer to section 8.11.1

(6) Local tolerability to be investigated 2 hours after each vaccination and additionally at the subsequent visits and prior to IMP administration.

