8.6 Follow up Period

8.6.1 Visit 6 (day 182 \pm 14 days)

Subjects will be asked to return to site for follow up Visit 6, 168 to 196 days (6 months) after Visit 1.

Blood samples will be collected for immunogenicity assessments (Chikungunya antibody ELISA and PRNT₅₀). For details on laboratory sampling and testing, see section 8.11.

The subjects are invited to return to study site for the final Visit 7 on study day 365 (\pm 14 days).

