8.10 End of Study

The end of study will be defined as the date of the last visit of the last subject. The study will then be stopped. For premature termination or suspension of the study, refer to section 8.9.1

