6.2.2 Derivations and Definitions

- All solicited and unsolicited Adverse Events up to day 56 (Visit 5) will be analyzed for the preliminary analysis. AE reporting and documentation is completed at Day 56. Thus all AE in the database are considered for the adverse event endpoints. In case of unexpected data change, new reported AEs or follow-up information, affected tables and/or listings may be repeated for the final analysis. Otherwise,

Adapted from:

STAT03_A Statistical Analysis Plan

Version 6.0, Effective Date 16-Feb-2018

Confidential and intellectual property of Assign DMB. No part of this document or its contents may be duplicated, referenced, published or otherwise disclosed in any form or by any means without prior written consent of Assign DMB.

Page 16 of 29

06CJDX

adverse event tables are not repeated at the final analysis. This decision may be done in a DRM prior to database closure, see [Section 2.9](#).

- Percentages for AE rates are based on N (treatment group totals).
- Medical Conditions/symptoms noted prior to first IMP administration will be reported as medical history and not as adverse events. In case of an incomplete start date where it cannot clearly be decided if the Adverse Event started before the first IMP the Adverse Event will be considered to be started before first IMP.
- An Adverse Events is considered to be related to study treatment if “Relationship to Study Treatment” is answered with “definitely”, “probably” or “possibly” or the causality is missing.
- Adverse Events where an action was taken are considered if “Action taken with Study Treatment” is answered with “Second IMP Administration Delayed” or “Second IMP not Administered”.
- Tables showing “severe” events will include events with grade 3 or 4 or missing grade.
- In tables showing subjects with AEs by maximum severity, subjects will be counted only in the highest grading category, but events will be counted in each reported grading category.
- In tables showing AEs by causality, subjects will be counted only in the strongest relationship category, but events will be counted in each category.

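### For adverse events still open at Visit 5, including arthralgia, follow-up to an outcome is promised but no later status check is scheduled

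*Combined protocol and SAP*

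**What the plan says.** **Follow-up to an outcome.** Protocol section 10.4 says that AEs "will be followed until the subject has recovered, stabilised, recovered with sequelae or died until end of the study". Section 8.10 sets the cap: "The end of study will be defined as the date of the last visit of the last subject". Each subject's last scheduled visit is Visit 7 (day 365 ± 14). Under section 10.1.8, 'Stabilised' may be used only once the subject has completed the study, and 'Ongoing at final examination' refers to the subject's last visit. Section 10.2 gives each event one eCRF page, running from start to resolution and including an end date.

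**No scheduled collection after Visit 5.** Footnote 3 to protocol Table 2 (section 6.5), repeated in SAP section 1.6, reads: "At Visit 6 and 7 AEs will not be recorded as subjects are allowed to participate in other clinical studies during the follow-up period". Of Visit 6, section 8.6.1 says: "Blood samples will be collected for immunogenicity assessments". Section 8.6.2 for Visit 7 adds only serum for passive transfer. Neither section contains an AE step.

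**Analysis.** SAP section 6.2.2 states: "AE reporting and documentation is completed at Day 56". It then allows affected tables and listings to be repeated at the final analysis if data change or if new AEs or follow-up information arrive. SAP sections 2.1 and 2.9 contain similar provisions. In SAP section 7, the AE tables (1.4.2 to 1.4.27) and AE listings (1.4.3 to 1.4.32) are marked n/a for the final analysis. Listing 1.4.4 carries the outcome and the ongoing-at-final-examination field.

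**The concern.** The protocol commits to a follow-up that its own visit schedule does not deliver. An AE open at Visit 5 belongs to a subject who is expected back on site twice, at about six and twelve months, yet nobody is instructed to ask about it then. Its record may simply stay open.

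This matters most for arthralgia. Section 4.6 names it as the AE of special interest, because an earlier live chikungunya vaccine was associated with transient joint pain. For such an event, duration and resolution carry much of the information. The trial also tests a dose that section 4.5 describes as an increase, and section 4.4.1 reports that AEs rose with dose in phase I.

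There is a coding problem as well. Listing 1.4.4 is scheduled only for the Day 56 analysis. For a subject continuing to Visit 7, the two outcome terms tied to study completion or last visit cannot be properly assigned when that listing is produced.

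**Working it through.** **Inputs**
- Visit 3 (second injection): day 23 to 33 (protocol 8.5.3).
- Visit 5: day 51 to 61 (8.5.5).
- Visit 6: day 168 to 196 (8.6.1). Visit 7: day 351 to 379 (8.6.2).
- Phase I joint pain or arthralgia: 10/42 overall, 5/42 rated as related (4.4.1).
- Planned sample: 60 subjects.
- Three months taken as 90 to 92 days (my conversion).

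**1. The plan's own figures.** The synopsis gives 8 weeks of treatment and 44 weeks of follow-up: 56/7 = 8 and (365 − 56)/7 = 44.1. Section 11.5 gives 28 days of follow-up after each treatment; after the second injection, 56 − 28 = 28. Both agree with the schedule.

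**2. Observation allowed by the windows.** After the first injection, the last scheduled AE status falls on day 51 to 61. After the second, the shortest span is 51 − 33 = 18 days and the longest is 61 − 23 = 38 days. Scheduled AE recording covers 56/365 = 15% of a subject's year; the other 309 days have no AE visit.

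**3. Comparison with the only duration threshold in the documents.** Section 4.2 says that chronic "disease is defined by symptoms that persist for more than 3 months". For an event starting at the first injection, that mark falls 90 − 56 = 34 to 92 − 56 = 36 days after a day-56 visit, or 29 to 31 days after the latest permitted Visit 5 (day 61). For an event starting at a second injection on day 28, it falls on study day 118 to 120. No scheduled AE visit reaches it.

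**4. What a status check at the existing visits would reach**

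| Visit | Days after injection 1 | Days after injection 2 |
|---|---|---|
| 5 (last scheduled now) | 51–61 | 18–38 |
| 6 | 168–196 | 168 − 33 = 135 to 196 − 23 = 173 |
| 7 | 351–379 | 351 − 33 = 318 to 379 − 23 = 356 |

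**5. How many subjects.** At the phase I rates, 60 × 5/42 = 7.1 to 60 × 10/42 = 14.3 subjects would report arthralgia. The documents do not give the share still open at Visit 5. If it were 0% to 20% (an assumption for illustration only), the count would be 0 to 1.4 at the lower rate and 0 to 2.9 at the higher. The phase I rates are an imperfect guide: they include control subjects and come from injections on days 0, 28 and 90. Section 4.4.1 also reports that all phase I AEs had recovered by study end and that musculoskeletal pain had fallen to one subject by that trial's visit 5. This points to the low end of the range.

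**The case against.** The sections can be read together. Section 10.2 limits which AEs are recorded to those arising in the treatment period, and 10.4 governs follow-up of those events. The reason given in footnote 3, possible participation in other studies, fits new events, so the footnote may exclude only those. Section 10.2 asks for follow-up information as necessary, section 8.8 allows unscheduled visits that are entered in the eCRF, and SAP section 6.2.2 lets late information trigger repeated outputs. For SAEs, sections 10.3 and 10.4 add proactive follow-up through the safety desk. No endpoint concerns AE persistence, and the AE endpoints end at day 56 by design.

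Much of this stands. It shows that later follow-up is possible. It does not schedule it: the documents never say that footnote 3 covers new AEs only, no visit instructs anyone to check open events, and a rerun remains optional.

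It also rules out several stronger readings that a reader might infer:
- *Every AE must be followed to Day 365.* Section 10.4 stops at outcome; end of study is only the cap.
- *The trial cannot separate transient from persistent arthralgia.* An event resolved by Visit 5 has an end date and is identifiable as transient.
- *The SAP closes the AE data for good.* It provides for repeats.
- *Three months is a trial criterion.* It is a background definition for natural chikungunya disease. Section 4.6 notes that the vaccine contains no live chikungunya virus and that chikungunya-like symptoms are not expected.

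**Conclusion.** The point holds for AEs still ongoing at Visit 5. Section 10.4 and the outcome definitions in 10.1.8 need AE status up to an outcome, study completion or last visit. Footnote 3, sections 8.6.1 and 8.6.2 and SAP section 6.2.2 provide no scheduled way to obtain it. What may be lost is the resolution or persistence of those events beyond the Visit 5 limits worked out above.

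The size is a matter of completeness of safety data. No primary endpoint, test or sample-size argument is affected. The number of affected arthralgia cases cannot be derived from the documents, and zero is plausible. The conclusion does not depend on that count: it rests on the conflict between the sections and on the absence of any instruction to check open events. With 12 subjects per group, even one unresolved case would be worth knowing about.

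**What to change.** 1. Reconcile protocol sections 10.4, 10.1.8 and 8.6, footnote 3 (protocol 6.5 and SAP 1.6) and SAP section 6.2.2. State in footnote 3 that only new AEs are excluded at Visits 6 and 7.
2. At Visits 6 and 7, record the status, end date and outcome of each AE that was open at Visit 5, and note any participation in another trial since then. Keep those eCRF pages open until Visit 7.
3. Make listings 1.4.3 and 1.4.4 a fixed part of the final analysis, restricted to or flagging these AEs, with arthralgia identified.

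**Cost.** A few minutes of site time per affected subject at visits that already take place, and two listings rerun. No extra visit, sample or new-AE collection is needed. End dates obtained months later may suffer from recall, and participation in another trial may alter an event's course. Recording that participation makes the second limitation visible but does not remove it.
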